#### 5.2.4 Secondary analysis for primary outcome

Model shown in Section 5.2.2 will be performed on per protocol population.

#### 5.2.5 Analysis of secondary outcomes

To quantify treatment effect estimate and within arm change between each measuring time for the number of intrusive memories at week 8 and other secondary outcome measures. MLM will be performed with baseline measure, binary arm status, following up time and interaction of arm  $\times$  time included as fixed effect covariates, participant as level 2 analytical units (European Medicines Agency, 2013). ML linear regression will be used for normally distributed continuous data (Vickers and Altman, 2001), ML logistic regression will be used for binary outcomes. Multilevel Poisson regression will be performed for count data. Skew continuous measure will be transformed for ML linear regression model if needed with reference on data exploratory results, (see for example Manning and Mullahy, 2001; Ives, 2015; Curran-Everett, 2018). For count data, ZIP model will be performed if there are extreme 0 counts or negative binomial model will be conducted if the data is over

dispersed. The treatment effect estimate and its 95% CI together with significance level for between group comparison will be derived from MLM, the estimate and its 95% CI will be presented for the estimate of within group change from baseline to each follow-up time.

If MLM result showed non-significant level-two variance estimate, or any model convergence issues, conventional single level regression will be performed with cluster-robust standard error reported for treatment effects estimate.

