- Randomise participants and will issue email/text reminders to participants and study researchers when study-related activities are due.
- Collect intrusive memory diary and intrusive memory rating data during the run-in week and at week 4 (Day 22 to 28) for all participants and at week 8 (Day 50 to 56) for participants in the delayed intervention arm.
- Collect self-reported outcome measurement data at baseline, 4 weeks (Day 28) and 8 weeks (Day 56) in both arms.

The primary comparison will be a between-groups comparison of the number of intrusive memories recorded during week 4 (i.e. from day 22 to 28; which is post intervention in arm 1 and pre-intervention in arm 2), controlling for the number of intrusive memories recorded during the run-in week. Secondary comparisons will be within-group comparisons of the number of intrusive memories in the run-in week (pre-intervention) and week 4 (Day 22 to 28) (post intervention; immediate intervention arm only) and week 4 (Day 22 to 28) (pre-intervention) and week 8 (Day 50 to 56 +7 days) (post intervention; delayed intervention arm only). After the first intervention session, both arms will have continued access to the intervention for the duration of the study period.

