## **5.4 Screening Visit Procedures (Run-in-week)**

### **5.4.1 Intrusive memory diary**

After obtaining informed consent, participants will be asked to complete a daily online intrusive memory diary for a run-in period of one week. Participants will be asked to record a simple count of the number of intrusive memories they

have each day. The intrusive memory diary is based on that used in previous studies of the brief behavioural intervention (e.g. Holmes et al., 2009; James et al., 2015; Iyadurai et al., 2018), and adapted for digital delivery using ePRO. Participants will be sent a link to create a personal, password-protected user account to access ePRO. Each day they will receive a reminder (by text/email) to log in and complete their intrusive memory count. Intrusive memories are defined as “mental images from a traumatic event that pop suddenly into your mind when you don’t want them to” and instructions will include a link to a video explaining what intrusive memories are. Each day, the participant is asked to indicate if they have had any intrusive memories (yes/no) and if so, how many. This type of daily online intrusive memory diary has already been piloted with NHS staff with high (99.4%) completion rates (Kubickova et al., in prep). At the end of the week, they will be asked to rate how accurately they think they completed the diary over the last week (on an 11-point scale from 0 = not at all accurately to 10 = extremely accurately).

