#### 5.7.5 Week 8 (D50 to D56)

Immediate Intervention Arm:

- All participants in the immediate intervention arm will be asked to complete the intrusive memory rating at the end of week 8 (D56).
- All participants in the immediate intervention arm will be asked to complete the online questionnaires at the end of week 8 (D56), including IES-R, PCL-5 4-item version, GAD-2, PHQ-2, SCI, PSYCHLOPS, WHODAS, EQ-5D-5L, Number of sick days, Scale of

Work Engagement and Burnout (SWEBO), Intention to leave job in addition to changes to health and work on ePRO.

Delayed Intervention Arm:

- All participants in the delayed intervention arm will be asked to complete the online questionnaires at the end of week 8 (D56+7 days), including IES-R, PCL-5 4-item version, GAD-2, PHQ-2, SCI, PSYCHLOPS, WHODAS, EQ-5D-5L, Number of sick days, Scale of Work Engagement and Burnout (SWEBO), Intention to leave job, in addition to changes to health and work on ePRO.
- All participants in the delayed intervention arm will have continuous access to the intervention and the record of intrusive memories at the end of week 8 (D56+7 days) will be asked to complete the daily intrusive memory diary during week 8 (D50 to D56) on a daily basis followed by intrusive memory ratings at the end of week 8 (D56) on ePRO.

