## 5 Analysis

### 5.1 Outcome definitions

#### 5.1.1 Primary, Secondary, and Tertiary Outcomes

The number of intrusive memories of traumatic event(s) are recorded by participants in a brief daily diary for 7 days during the run-in week (Day 0 to 6) and week 4 (Day 22 to 28) of the intervention. The primary endpoint is the total number of intrusive memories of traumatic event(s) reported in week 4 (i.e. from Day 22 to 28 post first intervention session in immediate intervention arm or equivalent time frame in delayed intervention arm). We are interested in the between-groups comparison while controlling for number of intrusive memories during the run-in week.

**Table 2:** Summary of the outcome measures

Outcome measure	Scale description	Items & scoring	Baseline	Week 4	Week 8
Primary endpoint					
Number of intrusive memories of traumatic event(s)	Number of intrusive memories of traumatic event(s) recorded by participants in a brief diary daily for 7 days.	Total number of intrusive memories of traumatic events reported in Week 4 (between-groups comparison controlling for number of intrusive memories during the run-in week).	X	x	
Secondary endpoints					
Number of intrusive memories of traumatic event(s)	Number of intrusive memories of traumatic event(s) recorded by participants in a brief diary daily for 7 days.	Total number of intrusive memories reported in Week 4 compared to run-in week for the immediate group and Week 8 compared to Week 4 for the delayed group (within-group comparisons).	X	x	x

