### **5.2.6 Summary of table and figures**

A summary of tables and figures is provided as additional information to accompany the analyses specified in this SAP. At a minimum, analyses will be summarized and presented in three tables and two figures.

The first table will involve a summary of all participant demographic and baseline characteristics with n (non-missing sample size), mean, standard deviation, median, maximum and minimum for continuous variables, the frequency and percentages (based on the non-missing sample size) of observed levels for all categorical measures.

The second table will involve data for the total number of reported intrusive memories for the three time points (run-in week, Week 4, Week 8), with n (non-missing sample size), mean, standard deviation, effect sizes for continuous variables (effect size (Cohen's d, with 95% confidence intervals). This will be accompanied with a figure illustration for the primary outcome measure (Week 4).

The third table summarize secondary and other outcome measures by arm, and across follow-up times if repeatedly collected (e.g., 4 weeks, 8 weeks), with n (non-missing sample size), mean, standard deviation, median, maximum and minimum for continuous variables, the frequency and percentages (based on the non-missing sample size) of observed levels for all categorical measures.

A CONSORT diagram will be provided to illustrate the number of participants involved in each phase and of the trial (e.g., enrolment, intervention allocation, completion of primary- and secondary outcomes and follow-ups).

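### SAP 5.2.5 promises a week-8 treatment effect on the intrusive-memory count, but only the delayed arm keeps a week-8 diary, and the stated model also omits a planned within-arm change

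*SAP*

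**What the plan says.** **Collection.** Protocol 3.1 has the ePRO diary completed by everyone in the run-in week and week 4, and "at week 8 (Day 50 to 56) for participants in the delayed intervention arm". Protocol 5.7.5 gives the immediate arm the end-of-week ratings and the questionnaires at week 8, but no diary. Appendix 1 tags the week-8 diary entry as delayed arm. The separate daily record in i-spero is requested only for each participant's four-week intervention period (Protocol 5.6.1 and 5.7.1), so it is not a planned week-8 source for the immediate arm.

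**Endpoints.** Protocol 9.2 and SAP Table 2 define two secondary count comparisons, both within arm: immediate arm, run-in against week 4; delayed arm, week 4 against week 8. Protocol 11.3.4 places the group comparison at the fourth week.

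**Analysis.** SAP 5.2.5 states its aim as "To quantify treatment effect estimate and within arm change between each measuring time for the number of intrusive memories at week 8", together with the other secondary outcomes. The model has the baseline measure, arm, follow-up time and arm × time as fixed effects and participant as level 2. On outputs it says "The treatment effect estimate and its 95% CI together with significance level for between group comparison will be derived from MLM", and it promises a confidence interval for "the estimate of within group change from baseline to each follow-up time".

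**Presentation.** SAP Table 2 marks the week-8 count with an unqualified cross, although the feedback questionnaire row of the same table carries arm labels. The second results table in SAP 5.2.6 covers three time points for the count, with no arm restriction.

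**The concern.** An arm × time model with two follow-up times needs both arms observed at both times if the arm effect is to be read at each. For the diary count one of those four cells is empty by design. An analyst following SAP 5.2.5 literally would be asked for a week-8 treatment effect, and for an immediate-arm change to week 8, that no data can supply. Software will usually remove a redundant term and print the rest, so the gap may not be noticed and a week-4 quantity could be reported under a week-8 label.

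There is a second gap. The first secondary objective includes the immediate arm's change in count from run-in to week 4. In the stated model the run-in count is only a covariate, so that change is not among the quantities estimated.

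**Working it through.** The plan states no figure for this point, so there is nothing to reproduce. The check is whether each promised quantity can be estimated from the scheduled data.

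**Scheduled diary cells** (Protocol 3.1, 5.7.5, Appendix 1):

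| Arm | Run-in | Week 4 | Week 8 |
|---|---|---|---|
| Immediate | yes | yes | none |
| Delayed | yes | yes | yes |

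**Step 1: the model as written.** With immediate = 1 and week 8 = 1, the follow-up mean is

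log μ = α + β₁·arm + β₂·run-in + β₃·week8 + β₄·(arm × week8).

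The observed cells have these rows (b is the run-in count):

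- delayed, week 4: (1, 0, b, 0, 0)
- delayed, week 8: (1, 0, b, 1, 0)
- immediate, week 4: (1, 1, b, 0, 0)

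The last column is zero throughout. The design has 5 columns and rank 4; leaving out the covariate, it has 4 columns and rank 3. A contrast can be estimated only if it lies in the row space:

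| Contrast | Combination | Estimable |
|---|---|---|
| Arm effect at week 4 | β₁ | yes |
| Delayed arm, week 4 to 8 | β₃ | yes |
| Arm effect at week 8 | β₁ + β₄ | no |
| Arm × week 8 | β₄ | no |
| Immediate arm, week 4 to 8 | β₃ + β₄ | no |

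Each immediate-arm participant contributes one response row, the week-4 count. The run-in to week-4 change in that arm is therefore not a coefficient, or a combination of coefficients, in this model.

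**Step 2: run-in as a response.** With run-in as a third time point there are five observed cells and six parameters (intercept, arm, week 4, week 8, arm × week 4, arm × week 8), and the rank is 5. The immediate arm's run-in to week 4, the delayed arm's run-in to week 8 and week 4 to week 8, and the week-4 arm effect can now be estimated. The week-8 arm effect and the immediate arm's run-in to week 8 still cannot.

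**Step 3: what software would print.** With immediate = 1 the interaction column is all zeros and is removed. With delayed = 1 the week-8 and interaction columns are identical, and a program may keep either. The fitted cell means do not change, but in the second case the delayed arm's own week-4 to week-8 change could be labelled as an arm × time effect.

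A Poisson simulation with 20,000 participants, a true week-4 arm rate ratio of 0.50 and a true delayed-arm week-4 to week-8 ratio of 0.50, with the interaction dropped, gave:

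| True week-8 arm rate ratio | Fitted arm rate ratio | Fitted delayed-arm week-8 ratio |
|---|---|---|
| 1.0 | 0.505 | 0.497 |
| 2.0 | 0.507 | 0.500 |
| 0.6 | 0.503 | 0.496 |

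The arm coefficient recovers the week-4 effect and does not respond to what happens at week 8. The delayed-arm contrast is recovered correctly.

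**Step 4: the SAP's own safeguards.** The fallback in 5.2.5 (single-level regression with cluster-robust errors) changes the variance and leaves the fixed effects as they are. SAP 5.3 describes imputation for diaries at baseline or week 4, so it neither covers the unscheduled cell nor says it should stay empty.

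**The case against.** The strongest reply is that no defined endpoint is lost. The objectives, Protocol 9.2 and 11.3.4, and SAP Table 2 plan exactly two secondary count comparisons, both within arm, and none asks for an arm comparison of counts at week 8. The opening sentence of SAP 5.2.5 is generic: it also covers the questionnaires, for which both arms have week-4 and week-8 data and the model is of full rank. Read with Table 2, it is loose drafting. The likely consequence is a mislabelled estimate, since the fitted cell means do not depend on which redundant term is dropped. The omission of run-in to week-4 change also has a different cause: it follows from using baseline only as a covariate, not from the absent diary.

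Most of this stands, and it limits the point to the SAP's analysis text and tables. It does not remove the point. SAP 5.2.5 names the week-8 count specifically, and it is the section that will be programmed. The covariate-only baseline leaves one of the two planned count contrasts outside the stated model, whatever the cause.

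A reader might infer that durability of the intervention goes unmeasured. The documents do not support that. At week 8 the immediate arm completes the intrusive memory ratings (Protocol 5.7.5), which include a 7-point past-week frequency item (SAP Table 2), and the IES-R with its intrusion subscale. Persistence of the diary count itself is unobserved in that arm, but the protocol sets no explicit objective for it and lists limiting participant burden as an aim (Protocol 1.3.2).

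**Conclusion.** The point holds for the diary count as SAP 5.2.5 is written. There are no scheduled week-8 counts in the immediate arm (about 75 participants at full enrolment), so the week-8 arm contrast, the arm × week-8 term and any immediate-arm change to week 8 carry no information at any sample size. The planned immediate-arm run-in to week-4 change is not a parameter of the stated model. Week-8 persistence in that arm is seen only indirectly.

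It would be tempting to say that the trial has no estimable treatment effect over time. That goes too far: the primary analysis is a separate single-level model of week-4 counts (SAP 5.2.2), and the week-4 arm effect and the delayed-arm week-4 to week-8 contrast can both be estimated.

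The conclusion rests on the diary schedule in the protocol being followed and on the i-spero record not being used as a substitute count. It does not depend on effect size, variance or power. It is worth correcting before database lock; it does not alter the primary result.

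**What to change.** In SAP 5.2.5, for the diary count only:

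1. Remove the week-8 between-arm effect and the arm × week-8 term.
2. Fit only the five observed arm-by-week cells, with the run-in count as a response and no longer as a covariate.
3. Report the two planned within-arm contrasts, immediate run-in to week 4 and delayed week 4 to week 8, with standard errors robust at participant level. Section 5.2.5 already names cluster-robust errors as its fallback.
4. Mark week 8 as delayed arm only in SAP Table 2 and in the second results table of 5.2.6, and state that the unscheduled immediate-arm cell is not to be imputed.
5. Add a caution. Eligibility requires at least three intrusive memories in the run-in week, so run-in counts are truncated from below. The run-in to week-4 change therefore includes regression to the mean and should be read as within-arm change, not as a treatment effect.

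The cost is SAP wording and a small change to the analysis script; no new data are needed.

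Opening the week-8 diary to the immediate arm is optional. It would bring the design to full rank and describe persistence. By then both arms have been offered the intervention, and Protocol 5.7.4 leaves it available to the immediate arm in weeks 5 to 7, so the comparison would be early against late start, not intervention against usual care. It would add seven daily entries per participant and need an amendment. The SAP is version 3.0 of June 2022, and the documents do not show how many immediate-arm participants had already passed week 8, so the data might be partial.

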### **5.2.6 Summary of table and figures**

A summary of tables and figures is provided as additional information to accompany the analyses specified in this SAP. At a minimum, analyses will be summarized and presented in three tables and two figures.

The first table will involve a summary of all participant demographic and baseline characteristics with n (non-missing sample size), mean, standard deviation, median, maximum and minimum for continuous variables, the frequency and percentages (based on the non-missing sample size) of observed levels for all categorical measures.

The second table will involve data for the total number of reported intrusive memories for the three time points (run-in week, Week 4, Week 8), with n (non-missing sample size), mean, standard deviation, effect sizes for continuous variables (effect size (Cohen's d, with 95% confidence intervals). This will be accompanied with a figure illustration for the primary outcome measure (Week 4).

The third table summarize secondary and other outcome measures by arm, and across follow-up times if repeatedly collected (e.g., 4 weeks, 8 weeks), with n (non-missing sample size), mean, standard deviation, median, maximum and minimum for continuous variables, the frequency and percentages (based on the non-missing sample size) of observed levels for all categorical measures.

A CONSORT diagram will be provided to illustrate the number of participants involved in each phase and of the trial (e.g., enrolment, intervention allocation, completion of primary- and secondary outcomes and follow-ups).

### **5.3 Missing data**

Exploratory data analysis will be used to assess the level of missing data for each participant. As the intrusive memory diary data is collected sequentially over time (either at baseline or at week 4), we will use time series methods (e.g. Chatfield, 2003) and an expectation-maximisation algorithm (Dempster, Laird and Rubin, 1977) to impute missing values (see also National Research Council., 2010) .

Initial missing values will be imputed by taking expectations across a participant's available diary data. Using Poisson likelihood and correlated errors, we maximise over this 'full' data set to provide updated expected values for the missing data. We will iterate over these latter steps until convergence in values of missing data (to a pre-determined threshold) is achieved.

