### **Definition of protocol deviations:**

A full list of protocol deviations will be denoted prior to unblinding of treatment including:

1. Non-completion of the primary outcome measure
2. Non-completion of guided intervention session/non-adherence to the intervention (as defined above).

All protocol deviations will be summarised, using the number (%) of participants by treatment group with details of type of deviation provided. The patients that are included in the ITT analysis data set will be used as the denominator to calculate the percentages. No formal statistical testing will be undertaken. Protocol deviations are classified prior to unblinding of treatment. A blinded list of protocol deviations will be shared with the statistician after the data base lock is reached.

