### **3.3 Analysis populations**

All analyses will be conducted on an intention to treat (ITT) basis. The ITT is defined as all randomised participants. The per-protocol analysis set consists of subjects for whom there are no significant adherence and protocol deviations according to the definition in previous Section 3.2. The Per Protocol Population (PP) are used for sensitivity analyses and will be defined at the Data Review Meeting.

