### **4.3 Recruitment**

A CONSORT flow diagram will be used to summarise the number of patients who were:

- assessed for eligibility at screening
  - eligible at screening
  - ineligible at screening\*
- eligible and randomised
- eligible but not randomised\*
- received the randomised allocation
- did not receive the randomised allocation\*
- randomised and included in the primary analysis
- randomised and excluded from the primary analysis\*

\*Reason will be provided in CONSORT Diagram.

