## 5.2 Analysis methods

All primary and secondary analyses will be conducted on an intention to treat (ITT) basis (European Medicines Agency, 2015). The ITT is defined as all randomised participants. Single level generalised linear modelling will be performed for the primary analysis and multilevel modelling (MLM) will be performed for secondary analyses to quantify the treatment effect, and its precision on all outcome measures. The details on descriptive statistics for all variables, frequentist analytical modelling for primary outcome and secondary outcomes are presented here in this section.

Qualitative analysis plans are beyond the scope of this document.

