### 5.2.2 Testing the treatment effects for primary outcome

To quantify treatment effect estimate and its 95% CI on primary outcome, Poisson regression will be performed with baseline measure and binary arm status included as fixed effect covariates. Zero inflated Poisson (ZIP) will be performed if there are extreme 0 counts or negative binomial model will be conducted if the data is over dispersed, with reference to data exploratory results (see Blasco-Moreno *et al.*, 2019).

For the Poisson generalised linear model to model the total number of intrusive memories recorded in week 4 using a canonical link function (logarithm), Let  $n$  be the number of participants which we are analysing, then for each participant  $i = 1, \dots, n$  we denote:

- $Y_i$  to be the random variable representing the primary endpoint (total number of intrusive memories in week 4).
- $Baseline_i$  to be the total number of intrusive memories recorded during the run-in week.
- $ARM_i$  to represent whether the participant is in the immediate intervention arm or the delayed intervention arm (control arm).

The model is as follows, where  $\alpha, \beta_1, \beta_2$  are our unknown model parameters.

$$Y_i \sim \text{Poisson}(\mu_i)$$

$$\log(\mu_i) = \alpha + ARM_i\beta_1 + Baseline_i\beta_2$$

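### SAP 5.3 fills missing diary counts with a single set of expected values and 5.2.2 allows nothing for that uncertainty; this matters only if wholly missing week-4 diaries are filled

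*SAP*

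**What the plan says.** - **Imputation (SAP 5.3).** The start is the participant's own record: "Initial missing values will be imputed by taking expectations across" whatever diary entries that participant made. A Poisson likelihood with correlated errors is then maximised over the filled data "to provide updated expected values for the missing data. We will iterate over these latter steps until convergence in values of missing data". The section names no arm term, no random draws and no variance correction. It gives no rule for a participant with no week-4 entries.
- **Primary model (SAP 5.2.2).** "To quantify treatment effect estimate and its 95% CI on primary outcome, Poisson regression will be performed", with arm and run-in count as covariates and zero-inflated or negative binomial alternatives. The sample is described only as "be the number of participants which we are analysing".
- **Analysis set (SAP 3.3).** "All analyses will be conducted on an intention to treat (ITT) basis. The ITT is defined as all randomised participants". SAP 5.2 repeats it: "The ITT is defined as all randomised participants".
- **Signs of exclusion.** The CONSORT list in SAP 4.3 has a line for those "randomised and excluded from the primary analysis". SAP 3.2 lists "Non-completion of the primary outcome measure" as a protocol deviation.
- **Observed-data fit (SAP 5.2.3a).** This is a sensitivity analysis, so the primary fit uses the filled data. The item does not say whether a part-completed week counts as observed.
- **Expected completion (Protocol 5.4.1).** A pilot of this kind of diary had 99.4% completion. Neither document gives a rate for wholly missing weeks.

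**The concern.** An expected value is not an observation. Once 5.3 has converged, the model in 5.2.2 cannot tell a filled total from a recorded one. It counts the filled participants as full information, and it sees too little scatter because their totals carry no residual noise.

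For a missing day or two within a completed week the other days fix the total closely, and little is lost. For a blank week the only sources are a model or the participant's run-in diary. The first leaves the standard error too small. The second carries a pre-intervention count into a post-intervention outcome and so biases the effect.

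The SAP does not settle which of these applies, or whether such participants are in the primary analysis at all. Two analysts following it could report different primary results. These results are meant to inform the next trial (SAP 1).

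**Working it through.** **Inputs.** From the documents: up to 150 participants, 75 per arm, two-sided 5% level, log-link count model with arm and run-in count. There is no stated missing-data figure to reproduce. Assumed: 5%, 10% or 20% of week-4 diaries wholly missing (7.5, 15 or 30 of 150), completely at random within arm.

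**1. Fill from a model with arm: effect on the SE.** In a Poisson log-linear model, filled values equal to the fitted values add nothing to the score equations, so the estimate does not move. The information is nevertheless summed over everyone, so SE(filled)/SE(observed) ≈ √(1−m): √0.95 = 0.975, √0.90 = 0.949, √0.80 = 0.894. A negative binomial fit loses more, because the filled totals also lower the estimated dispersion. The simulated ratios were 0.94, 0.89 and 0.78. If the SE is a fraction r of its proper size, coverage is 2Φ(1.96r) − 1:

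- r = 0.94: 93.5%
- r = 0.89: 91.9%
- r = 0.78: 87.4%

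**2. Fill from the run-in diary: effect on the estimate.** Take assumed means of 15 at run-in, 10 in week 4 (delayed) and 5 in week 4 (immediate), so the true rate ratio is 0.50. With a share m filled at the run-in level:

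- m = 5%: (0.95×5 + 0.05×15)/(0.95×10 + 0.05×15) = 5.5/10.25 = 0.537
- m = 10%: 6.0/10.5 = 0.571
- m = 20%: 7.0/11.0 = 0.636

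Now let missingness differ by arm:

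- 20% immediate, 5% delayed: 7.0/10.25 = 0.683, further toward 1.
- 5% immediate, 20% delayed: 5.5/11.0 = 0.50, no net shift.
- The last pattern with no true effect (both week-4 means 10): 10.25/11.0 = 0.93, away from 1.

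**3. Simulation, negative binomial fits, 75 per arm.** Set 1: run-in negative binomial with mean 10 and size 1.5, at least 3; week-4 size 1 or 2, mean 0.8 or 1.0 times the run-in geometric mean; slope 0.7 on log run-in; 3,000 trials per cell. Set 2: run-in mean about 15, delayed week-4 mean about 10, dispersion 0.8; 1,500 trials.

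| Weeks missing | Arm-model fill, null coverage (set 1; set 2) | Run-in fill, true log RR −0.69 (set 1), coverage | Run-in fill, true RR 0.50 (set 2), coverage |
|---|---|---|---|
| 5% | 93%; 93.5% | −0.63 | 0.535, 91.7% |
| 10% | 90–92%; 90.9% | −0.57 to −0.59, 86–90% | 0.566, 88.1% |
| 20% | 86–87%; 86.1% | −0.47 to −0.51, 61–79% | 0.631, 64.9% |

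A further run widened the 10% range for the arm-model fill to 88–92%. In set 2 the type I error of that fill was 6.5%, 9.1% and 13.9%. The observed-data fit covered 93–95% in set 1.

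Unequal missingness, run-in fill, set 2: 20% immediate and 5% delayed gave 0.665 for a true 0.50. The reverse gave 0.504, and 0.941 under the null (type I error 7.7%). These agree with step 2.

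**4. Multiple imputation** with arm and run-in count. Set 1 at 10% and 20% missing: log RR −0.688 and −0.686, coverage 94.4% and 93.6%. Set 2: coverage 93.5–95.3%.

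**5. Where the harm vanishes.** With isolated days only (0.6–20% of days missing, filled from the same week), coverage was 94.3–94.9% without bias. If the pilot's 99.4% is taken as 0.6% of weeks missing (about 0.9 of 150 participants), step 2 gives 5.06/10.03 = 0.504 and step 1 gives √0.994 = 0.997.

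**Limits.** The simulations fill weekly totals; they do not run the SAP's day-level algorithm with correlated errors. Set 1 used log run-in count; the raw count, as written in 5.2.2, changed coverage by at most about 1 point.

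**The case against.** SAP 5.3 speaks of each participant's available entries, of sequential collection at baseline or at week 4, and of time-series methods. That reads most naturally as filling gaps inside a diary week, which is harmless. SAP 3.2, 4.3 and the sample wording in 5.2.2 fit exclusion of blank weeks. The only documented completion rate is 99.4%. Daily reminders (Protocol 5.4.1), paper capture of missed entries (Protocol 10.1), researcher help (Protocol Synopsis) and the follow-up voucher (Protocol 15.0) should all keep losses low. SAP 5.2.3(a) would expose a discrepancy, and Protocol 11.3 promises a preregistered script that may settle the details.

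Much of this stands. A reader might infer that the planned primary CI is wrong as it is; the documents do not support that, because they neither say that blank weeks are filled nor indicate that many will occur. A reader might also infer that the fill always pulls the effect toward zero; step 2 shows that this depends on which arm loses more diaries.

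What does not stand is the view that nothing needs changing. If blank weeks are excluded, the primary set is not all randomised participants. If they are kept, the stated method has no imputation variance. A sensitivity analysis can show a discrepancy but does not correct the primary CI. The script was not among the documents reviewed.

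**Conclusion.** The point holds conditionally. The stated method is a single fill followed by an ordinary CI, and it is unsafe for blank week-4 diaries, which the ITT definition brings into the primary analysis.

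- Filled from a model with arm: the estimate is sound, the CI too narrow. Null coverage is about 93% at 5% of weeks missing, 88–92% at 10% and 86% at 20%.
- Filled from the run-in diary: the estimate is biased. With similar missingness in both arms, −0.69 becomes about −0.57 at 10% and −0.48 at 20%. More missing in the immediate arm also pulls it toward zero. More missing in the delayed arm can leave a true effect almost unchanged and move a null result slightly away from zero.
- Isolated missing days, or very few blank weeks: negligible.

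The sizes rest on assumed counts, dispersion and missing-week rates, with missingness completely at random within arm. The direction of the run-in bias assumes that run-in counts exceed week-4 counts.

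A reader might add that Day 1, and so the week-4 window, is undefined for an immediate-arm participant who never has a guided session. That is a separate scheduling question and is not evidence for this point.

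**What to change.** 1. **Primary analysis.** Replace the single fill with multiple imputation from a count model containing arm, run-in count and any completed week-4 days (for example m = 20, Rubin's rules). Apply it to all randomised participants, including those with no week-4 diary, and cover missing run-in days. State that a blank week-4 diary is not filled from the run-in week alone.
2. **Population.** Align SAP 4.3 and the sample description in 5.2.2 with the ITT definition.
3. **SAP 5.2.3(a).** Keep it as the observed-data sensitivity analysis, defined as the count model on completed week-4 days with offset log(days completed/7). Participants with no completed days cannot enter it, since log 0 is undefined; say so. The offset matters: if 5% of days are missing, 1 − 0.95⁷ = 30% of participants miss at least one day. Restricting to complete 7-day diaries then raised the SE from 0.180 to 0.215 in simulation.
4. **EM fill.** Keep it only as a further sensitivity analysis, stating whether its model includes arm.
5. **Reporting.** Give missing days and missing whole weeks by arm.

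The cost is SAP wording and routine software, settled before missingness by arm is known. The CI will be wider than under an arm-model fill when whole weeks are missing (SE about 0.188 against 0.167 at 10%, 0.200 against 0.155 at 20%) and almost unchanged otherwise. Missing at random is still assumed.
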